6.6.2. IM Dosing

Participants receiving CAB LA and/or RPV LA are anticipated to be at risk for development of virologic resistance if ART is interrupted. The time period during which participants are at risk for development of virologic resistance may be determined by the period between when drug levels fall below therapeutic values and when they fall below levels which exert selective pressure on HIV. This time period will vary by ART agent and is dependent upon effective concentration, inhibitory concentration, and half-life. Plasma concentrations of both LA drugs may be measurable for more than one year following IM injections. Any interruption in IM dosing should be discussed with the Medical Monitor. Investigators should ensure that the participant initiates alternative highly active ART to minimize the risk of developing resistance as concentrations of CAB and RPV decline over time.

IM dosing is expected to occur during the week in which the participant’s projected visit falls (as according to the date of the first injection).

Since the first injection visit (Month 1) will determine the future injection visit schedule for participants, planning for the first injection visit date (within allowed visit windows) should take into consideration the availability of the participants to adhere to future visit windows (planned vacations, business trips, *etc.*).

CAB LA + RPV LA dosing for participants transitioning from oral CAB + RPV is as follows:

All injections should be planned as single injections per drug.

6.6.2.1. IM injections every 1 month:

On Day 1, participants will return to the clinic, take the last dose of their oral (CAB 30 mg + RPV 25 mg), and receive the first CAB LA (600 mg) + RPV LA (900 mg) injections (within 2 hours of the final oral dose of CAB + RPV).

The second injection will be administered at Month 2 (CAB LA 400 mg + RPV LA 600 mg, with all subsequent injections (CAB LA 400 mg + RPV LA 600 mg) occurring every 1 month thereafter. The dosing window for the second and third injections allow administration between -7 days of the proposed injection visit date but preferably not later than the target date (-7 days/ +0 days around the proposed visit date). Beginning on Month 4, a dosing window (± 7 days) for injections is stipulated. The Medical Monitor must be contacted to discuss individual participant case management if a dose must be administered outside of the window.

6.6.3. Oral Dosing

Any interruption in therapy (scheduling conflicts, life circumstances, *etc.*) during any oral dosing period that is greater than 7 consecutive days must be discussed with the Medical Monitor prior to resumption of therapy. The Medical Monitor must be contacted upon site staff becoming aware of resumption in therapy, if therapy was resumed without prior approval.

Visits for participants in LTFU are expected to occur as projected according to the last injection.

6.7. Intervention after the End of the Study

The investigator is responsible for ensuring that consideration has been given to the post-study care of the participant's medical condition, whether or not GSK is providing specific post-study intervention. Participants who have successfully completed IM dosing for 12 months will continue to have access to both CAB LA and RPV LA until study intervention is either locally approved and commercially available, the participant no longer derives clinical benefit, the participant meets a protocol-defined reason for discontinuation or until development of either CAB LA or RPV LA is terminated.

7. DISCONTINUATION OF STUDY INTERVENTION AND PARTICIPANT DISCONTINUATION/WITHDRAWAL

Participants permanently discontinuing study treatments prior to the Month 12 visit are considered to be withdrawn from the study treatments. Participants permanently discontinuing study treatments prior to the commercial availability of CAB LA + RPV LA visit are not considered to be withdrawn from the study because they will enter the long-term Follow-up Phase.

A participant may withdraw consent and discontinue participation in this study at any time at his/her own request. The investigator may also, at his or her discretion, discontinue the participant from participating in this study at any time (e.g., safety, behavioral or administrative reasons). If a participant withdraws from the study, he/she may request destruction of any samples taken, and the investigator must document this in the site study records. Withdrawn participants will not be replaced.

All participants who discontinue prematurely from the study will be asked for additional information to establish the reason for withdrawal.

Participants are not obligated to state the reason for withdrawal. However, the reasons for withdrawal, or failure to provide a reason, must be documented by the Investigator on the Completion/Withdrawal section of the electronic case report form (eCRF). Every effort should be made by the Investigator to follow-up participants who withdraw from the study.

Participants may have a temporary interruption to their study intervention for management of toxicities.

Participants may be prematurely discontinued from the study intervention for any of the following reasons:

- Adverse event / Serious adverse event
- Protocol deviation
- Intolerability of injections
- Participant lost to follow-up
- Participant or Investigator non-compliance;
- Termination of the study by the Sponsor
- At the request of the participant, Investigator, GSK or ViiV Healthcare;
- The participant requires concurrent prohibited medications during the course of the study. The participant may remain in the study if in the opinion of the Investigator and the medical monitor; such medication will not interfere with the conduct or interpretation of the study or compromise the safety of the participant.

Participants must be discontinued from study intervention for any of the following reasons:

- Virologic withdrawal criteria as specified in Section 7.1.3 are met;
- Participant requires substitution of ART;
- Participant requires substitution or dose reduction of CAB LA, RPV LA (oral bridging supply and potential for a second loading dose may be permissible following discussion with the Medical Monitor)
- Liver toxicity where stopping criteria are met and no compelling alternate cause is identified (see Section 10.6.2);

- Renal toxicity is met and no compelling alternate cause is identified;
- Corrected QT interval (QTc) >550 msec from three or more tracings separated by at least 5 minutes and considered causally related to IP. *Note: ECGs are not routinely conducted in this study.*
- Grade 4 clinical AE considered causally related to study drug;
- Participant has a Grade 3 or higher rash or Grade 2 rash with evidence of systemic involvement and no compelling alternative cause is identified.
- Participant withdrew consent

Safety data for all participants who receive any amount of study drug, including participants who withdraw from the study, will be included in evaluations of safety.

If a participant is prematurely or permanently withdrawn from the study, the procedures described in the Schedule of Activities Table, Section 1.5, for the in-clinic Withdrawal visit are to be performed. An in-clinic Follow-Up visit will be conducted 4 weeks after the last dose of study medication for participants with ongoing AEs, and serious adverse events (SAEs) related & not related to study drug and also any laboratory abnormalities that are considered to be AEs or potentially harmful to the participant, at the last on-study visit.

All data from the Withdrawal visit will be recorded, as they comprise an essential evaluation that should be done prior to discharging any participant from the study.

The following actions must be taken and documented in relation to a participant who fails to attend the clinic for a required study visit:

- a. The site must attempt to contact the participant and re-schedule the missed visit as soon as possible.
- b. The site must counsel the participant on the importance of maintaining the assigned visit schedule and ascertain whether or not the participant wishes to and/or should continue in the study.
- c. In cases where the participant is deemed ‘lost to follow up’, the investigator or designee must make every effort to regain contact with the participant (where possible, 3 telephone calls and if necessary a certified letter to the participant’s last known mailing address or local equivalent methods). These contact attempts should be documented in the participant’s medical record.
- d. Should the participant continue to be unreachable, only then will he/she be considered to have withdrawn from the study with a primary reason of “Lost to Follow-up”.

A participant may withdraw from study intervention at any time at his/her own request, or may be withdrawn at any time at the discretion of the investigator for safety, behavioral or administrative reasons. If a participant withdraws from the study, he/she may request destruction of any samples taken, and the investigator must document this in the site study records.

7.1. Discontinuation of Study Intervention

Participants unable to manage drug toxicity or tolerate investigational product (either formulations of CAB or RPV,) must have IP discontinued. Any participant receiving at least one dose of CAB LA and /or RPV LA who discontinue IP / Withdraw will initiate treatment with HAART enter the LTFU Phase for an additional 52 weeks of follow up.

7.1.1. QTc Stopping Criteria

A participant who has a QTc interval >550 msec considered causally related to IP will be withdrawn from the study. The QTc should be based on averaged QTc values of triplicate electrocardiograms obtained over a brief (e.g., 5 to 10 minute) recording period.

If an alternative cause of the QT prolongation is determined (e.g., participant receiving drug known to cause prolonged QT or TdP), the IP may be restarted (or continued) after consultation and agreement with the Medical Monitor. RPV and RPV LA should not be administered to participants who are receiving a drug known to be associated with TdP.

When performing ECGs, the *same* QT correction formula *must* be used for *each individual participant* to determine eligibility for, and discontinuation from, the study. This formula may not be changed or substituted once the participant has been enrolled.

For example, if a participant is eligible for the protocol based on QTcB, then QTcB must be used for discontinuation of this individual participant as well.

Once the QT correction formula has been chosen for a participant's eligibility, the *same formula* must continue to be used for that participant *for all QTc data being collected for data analysis*. Safety ECGs and other non-protocol specified ECGs are an exception.

7.1.2. Virologic Failure

Only plasma HIV-1 RNA values determined by the central laboratory will be used to assess virologic failure.

7.1.3. Definition of Protocol-Defined Confirmed Virologic Failure

For the purposes of clinical management in this study, CVF is defined as:

Rebound as indicated by two consecutive plasma HIV-1 RNA levels ≥ 200 c/mL.

7.1.4. Managing Virologic Failure

Following study entry, no changes, or intensification of ART will be permitted prior to protocol-defined virologic failure, outside of the planned protocol regimens. Only plasma HIV-1 RNA values determined by the central laboratory will be used to assess virologic failure. Baseline plasma HIV-1 RNA is the assessment completed on study Day 1. The definition of confirmed virologic failure does not apply to participants in the LTFU Phase. These participants will be followed for the emergence of viral resistance.

Inadequate adherence or maladministration may be a cause for virologic failure and should be explored as a first step in the management of study participants (e.g., at the first indication of inadequate virologic response or rebound). Upon notification that a participant's HIV-1 RNA plasma level qualifies him/her as a suspected virologic failure (SVF), the Investigator should query the participant regarding intercurrent illness, recent immunization, or interruption of oral therapy.

7.1.4.1. HIV-1 RNA Blips

HIV-1 RNA “blips” are not usually associated with subsequent virologic failure [DHHS, 2018]. Although the implications of persistent HIV-1 RNA levels between the lower level of detection and <200 c/mL are unclear, the risk of emerging resistance is believed to be relatively low.

Participants with transient increases in HIV-1 RNA (‘blips’ HIV-1 RNA <200 c/mL) are not considered suspected virologic failures and do not require a change in therapy.

Participants who have a HIV-1 RNA ≥ 50 c/mL at the key analysis timepoints (Month 12, End of Study visit) should return for a repeat HIV-1 RNA as soon as possible but no later than 4 weeks after the date of the Month 12 or End of study visit, respectively such that the result falls within the same analysis window.

In order to better characterize HIV-1 RNA ‘blips,’ if there is a known reason / explanation for the blip (e.g., immunization, allergies, etc), the study team should be notified of the reason and case context.

If the Investigator has concerns regarding persistent low-level viremia (HIV-1 RNA ≥ 50 c/mL and <200 c/mL), the Medical Monitor should be contacted to discuss participant management. Following discussion with the Medical Monitor, additional viral load testing may be performed between visits to determine the appropriate participant disposition for the next scheduled visit.

7.1.4.2. Suspected Virologic Failure

Upon notification that a participant's HIV-1 RNA plasma level meets the definition of virologic failure, the Investigator should confirm the definition is met by initiating a repeat of the HIV-1 RNA assessment.

The following guidelines should be followed for scheduling confirmatory HIV-1 RNA testing in an effort to avoid false-positive results:

- Confirmatory testing should be scheduled within 2 to 4 weeks following resolution of any intercurrent illness, during which time the participant should receive full dose of all IP.
- Confirmatory testing should be scheduled at least 4 weeks following any immunization, during which time the participant should receive full dose of all IP.

- If therapy is interrupted* due to toxicity management, non-compliance, or other reasons, confirmatory testing should be scheduled 2 to 4 weeks following resumption of full dose of all IP.
- The participant should have received full dose of IP for at least 2 weeks at the time confirmatory plasma HIV-1 RNA testing is done.

*Note: treatment interruption guidelines above may not apply for participants on CAB LA + RPV LA treatment. The study team should be contacted to discuss any treatment interruptions for participants meeting the definition of virologic failure.

In addition, the Investigator should query the participant regarding intercurrent illness, recent immunization, or interruption of therapy.

Sites should contact the Medical Monitor to discuss individual participants, whenever necessary.

7.1.4.3. Confirmed Virologic Failure

Participants with CVF must be discontinued from study treatment. However, participants who have received at least one dose of CAB LA or RPV LA prior to confirming virologic failure will remain in the study on oral HAART in the LTFU Phase.

A plasma sample from the suspected virologic failure visit as well as Day 1 (if baseline HIV-1 RNA level ≥ 200 c/mL) will be sent for genotypic and phenotypic resistance testing and the result made known to the Investigator when available. A plasma sample from the confirmation visit will be obtained for storage. This sample may be used for possible future analyses, e.g., for genotypic and phenotypic analyses of participants who experience virologic failure.

For all participants who meet CVF, baseline and suspected virologic failure plasma samples with HIV-1 RNA level ≥ 200 c/mL will be analyzed in an attempt to obtain genotype/phenotype data on as many samples as possible. Plasma samples for storage will also be obtained at unscheduled visits including confirmation of CVF. Participants may continue to receive study drug at the discretion of the investigator until results of resistance testing are available at which time the participant must be discontinued from the study. Even if genotype/phenotype data cannot be generated, participant must also be discontinued from the study intervention.

If a participant is prematurely discontinued from the study intervention, the investigator must make every effort to perform the Withdrawal Visit evaluations outlined in the Schedule of Activities Table, Section 1.5. These data will be recorded as they comprise essential evaluations needed to be done before discharging any participant from the study.

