enrolled into the trial and subsequently withdrawn from the study, for any reason, may not be re-screened. Participants may be enrolled as soon as all eligibility requirements have been confirmed at the site. Patient study participants with an undetectable HIV-1 RNA (<50 c/mL) at Screen are eligible to enter this study. A single repeat viral load to determine eligibility may be allowed ONLY after consultation with the medical monitor. Should a participant be allowed a repeat, results of this repeat must be available prior to Day 1 of this study, therefore the time needed for scheduling the Day 1 visit, lab draws and lab analysis should be considered.

HIV-infected participants who meet all eligibility criteria will be switched at Day 1 from their pre-baseline regimen to an oral regimen for one month (CAB 30 mg + RPV 25 mg). Participants will return to the clinic, and if laboratory and clinical evaluations continue to support progression into the LA portion of the study, will take the last dose of their oral regimen (CAB 30 mg + RPV 25 mg), and receive the first CAB LA (600 mg) + RPV LA (900 mg) injections (within 2 hours of the final oral dose of CAB + RPV). All subsequent injections (CAB LA 400 mg + RPV LA 600 mg) will occur every month thereafter. Note: Patient study participants with \geq Grade 1 LFTs at screening and or day 1 must be discussed with the Medical Monitor prior to initiation of LA dosing; continuation in the study or progression onto LA dosing may require additional evaluations, including labs drawn after a period of oral dosing with CAB + RPV.

The dosing window for the second and third injection (Month 2 and Month 3) will be +0 / -7 days from the projected dosing visit; All subsequent injection windows (beginning at Month 4) will be +7/-7 days from the projected date of the visit. Doses outside of the window *may* be allowed with prior Medical Monitor approval.

Participants will continue CAB LA + RPV LA until:

- study intervention is locally approved and commercially available,
- the participant no longer derives clinical benefit,
- the participant meets a protocol-defined reason for discontinuation
- the development of either CAB LA or RPV LA is terminated
- participant withdraws consent
- investigator discretion
- participant or investigator non-compliance
- termination of the study by the Sponsor.

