Safety and efficacy assessments will be conducted as per the Schedule of Assessments. Dosing will occur according to the selected regimen.

If the intramuscular (IM) dosing regimen is discontinued as a result of an independent data monitoring committee (IDMC) review from the ongoing Phase 3 studies, any subsequent analysis, or any other programmatic analysis, those participants who have not met any clinical management criteria for discontinuation will be discontinued permanently from the study and will enter into the LTFU Phase of the study.

LTFU Phase –Following the IM Regimen Only

Any participant who receives *at least one* dose of CAB LA and/or RPV LA and discontinues the CAB LA + RPV LA regimen for any reason must remain on suppressive HAART for at least 52 weeks after the last dose of CAB LA and/or RPV LA in order to prevent selective pressure on HIV during the period of declining drug exposures and the potential for selection of resistant mutants. **Investigators must discuss the choice of the follow-up HAART regimen with the Medical Monitor prior to initiating the new regimen with the participant. HAART therapy should be initiated within 4 weeks after the last monthly injection, however if withdrawn due to virologic failure, HAART should be initiated as soon as virologic failure is confirmed. Discuss with medical monitor.** The Long-Term Follow Up period (LTFU) will begin the day of the last CAB LA and/or RPV LA dose and continue for 52 weeks. These participants will not complete a Withdrawal visit, but will instead move directly into the LTFU as per the Schedule of Activities, Section 1.5. In addition, for participants who withdraw during the LTFU, the final visit will be considered the study withdrawal visit.

Participants will be assessed with clinic visits at months 3, 6, 9, and 12 during the LTFU Phase. Female participants of child bearing potential must continue to use adequate contraception methods for the entire year of follow up.

In order to assure that participants have access to HAART during the LTFU, ViiV Healthcare may supply HAART or reimbursement may be provided as needed during this phase. The LTFU Phase may be shortened or terminated at any time during the study for various reasons, e.g., better understanding of risks of development of resistance as CAB and RPV exposures decline, end of study timings, etc.

Staff study participants

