Risk of Treatment Failure	
This study employs a novel 2 drug LA ART maintenance regimen for the treatment of HIV-1 infection that remains experimental. Both IM CAB and RPV have demonstrated antiviral activity in large clinical studies and the two-drug combination has demonstrated sustained antiviral activity in studies, LAI116482 and 200056.
 
Doses of the CAB LA and RPV LA have been selected to achieve exposures that are expected to maintain virologic efficacy on the basis of available data with the oral and LA formulations.
 
Due to administration error, it is possible that a participant could receive an inadequate dose of CAB LA or RPV LA. Sub-therapeutic concentrations of either CAB LA or RPV LA could lead to virologic failure and possibly the development of viral resistance.
	
 • Viral loads and CD4+ cell counts will be closely monitored throughout the study (maintenance and extension phases), allowing for early detection of failing treatment. Where confirmed virological failure occurs, participants would be discontinued from study drugs and transferred to an oral HAART regimen. • Plasma samples will be collected as needed during the injection Phase for determination of CAB and RPV concentration and possible pharmacokinetic correlation with virologic response.

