6. STUDY INTERVENTION

6.1. Study Intervention(s) Administered

The term ‘study intervention’ is used throughout the protocol to describe any combination of products received by the participant as per the protocol design. **Study intervention is defined as any investigational treatment(s), marketed product(s), placebo, or medical device(s) intended to be administered to a study participant according to the study protocol.** Study intervention may therefore refer to the individual study interventions or the combination of those study interventions.

Investigational product (IP) in this protocol refers to the investigational study drugs Oral Cabotegravir, Cabotegravir LA, Oral Rilpivirine and Rilpivirine LA. These will be supplied by GlaxoSmithKline/ViiV Healthcare and Janssen Pharmaceuticals, respectively.

Participants entering the Long-Term Follow-Up Phase will not have their selected HAART provided as clinical trial material. The selected HAART will be recorded on the Concomitant Antiretroviral Therapy (ConART) eCRF page.

Dosing and Administration

Day 1 to End of Study ⁺	
CAB + RPV LA Oral Lead-In	
Day 1 to Month 1 (two once daily tablets taken with food)	
 Take one tablet of CAB 30 mg + RPV 25 mg once daily
CAB + RPV LA	
First Injections (Loading Doses) – Month 1	
Month 1	
 Receive last dose of oral CAB + RPV regimen Receive CAB LA 600 mg given as 1 X 3 mL IM injection Receive RPV LA 900 mg given as 1 X 3 mL IM injection
Maintenance Injections – every one month following Loading Dose at Month 1	
Month 2 to End of Study ⁺ (two 2 mL injections every month)	
 Receive CAB LA 400 mg given as 1 X 2 mL IM injection Receive RPV LA 600 mg given as 1 X 2 mL IM injection
+Until locally approved and commercially available, the participant no longer derives clinical benefit, the participant meets a protocol-defined reason for discontinuation or until development of CAB LA or RPV LA is terminated	

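### Section 7.1.4.3 requires study treatment to stop at confirmed virologic failure, then lets it continue until resistance results without excluding another monthly injection, against the HAART timing in Section 1.3

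*Protocol*

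**What the plan says.** Section 7.1.4.3 begins with an unconditional rule: "Participants with CVF must be discontinued from study treatment". Anyone who has had at least one CAB LA or RPV LA dose then stays in the study on oral HAART in long-term follow-up (LTFU). Two paragraphs later, writing about participants who meet CVF, the section adds: "Participants may continue to receive study drug at the discretion of the investigator until results of resistance testing are available". At that point the participant must be discontinued from the study. If no genotype or phenotype can be produced, discontinuation from study intervention is still required, with no date attached.

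Four other places bear on this:

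- Section 1.3, LTFU Phase: "if withdrawn due to virologic failure, HAART should be initiated as soon as virologic failure is confirmed".
- Section 2.3.1, Risk of Treatment Failure: "Where confirmed virological failure occurs, participants would be discontinued from study drugs and transferred to an oral HAART regimen".
- Section 7, list of reasons for which study intervention must stop: "Virologic withdrawal criteria as specified in Section 7.1.3 are met".
- Section 6.1: investigational product "refers to the investigational study drugs Oral Cabotegravir, Cabotegravir LA, Oral Rilpivirine and Rilpivirine LA".

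**The concern.** Two rules in one section govern the same participant. One ends study treatment at CVF; the other lets it run on until a laboratory report arrives. Injections fall due monthly, and the permission does not distinguish oral tablets from depot doses. A site could therefore give a further CAB LA + RPV LA dose to someone whose two-drug regimen is already confirmed to be failing, and believe the protocol allows it.

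Such a dose is irreversible. Section 6.6.2 states: "Plasma concentrations of both LA drugs may be measurable for more than one year following IM injections". Section 1.3 explains suppressive HAART after the LA regimen as protection against selective pressure and resistant mutants while drug levels decline, and another dose of a failing regimen works against that purpose. It would also move the start of the 52-week LTFU, which is counted from the last LA dose.

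**Working it through.** This is mainly a comparison of texts. The only arithmetic is a rough count of those affected.

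**1. Is there a conflict, and with what?**

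| Place | What happens at CVF | When |
|---|---|---|
| 7.1.4.3, first sentence | Study treatment must stop | No day named |
| 7.1.4.3, later sentence | Study drug may continue at investigator discretion | Until resistance results |
| 1.3, LTFU Phase | HAART should start | As soon as failure is confirmed |
| 2.3.1 | Stop study drugs, transfer to oral HAART | No day named |
| 7 | Mandatory discontinuation | No day named |

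Only Section 1.3 fixes the timing, and it fixes it at confirmation. The later sentence of Section 7.1.4.3 moves the latest permitted stop to the resistance result. Those two cannot both be followed by a site that uses the permission. Sections 2.3.1 and 7 provide for no delay, but they exclude one only by implication.

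**2. Does the permission reach injections?** Section 6.1 counts Cabotegravir LA and Rilpivirine LA among the study drugs. Section 1.3 says that maintenance injections "will occur every month thereafter". I found no sentence that withholds a scheduled injection while resistance results are pending. Let T be the days from confirmation to the resistance result, and D the days from confirmation to the next due injection. If T > D, at least one further LA dose is permitted. The protocol gives no value for T, so the number of extra doses cannot be computed.

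**3. Does waiting affect the decision to stop?** No. Under Section 7.1.4.3 the participant stops whatever the result shows, and stops even if none can be generated. The result can inform only the choice of HAART.

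**4. How many participants?** As a rough guide, Table 10 (Section 4.3.2) gives virologic failures in the LATTE-2 Q4W arm: 1 of 115 at Week 48 and 0 of 115 at Week 96. Scaled to the planned maximum of 135:

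- Week 48: 135 × 1/115 = 1.17
- Week 96: 135 × 0/115 = 0

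That is about 0 to 1 participants. The Q8W arm is left out because this trial doses monthly. Snapshot failure at 50 c/mL is not the CVF definition, so this is an order of magnitude and not a forecast.

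**The case against.** The best defence is that the later sentence is a deliberate grace period: CVF requires discontinuation, and discontinuation falls no later than the resistance result. Several parts of this defence stand.

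- A reader might infer that Sections 2.3.1 and 7 flatly contradict the permission. They do not go that far, because neither names a day.
- A reader might call the permission open-ended. It ends when results arrive, and the next sentence requires discontinuation if none can be produced. What is missing is a calendar limit.
- A reader might cite Section 10.8.6.1, which lets a participant continue injections after a pregnancy loss unless the virologic withdrawal criteria are met. It says nothing about timing, so it neither supports nor refutes a grace period.
- No site is made to give a further injection. One that stops at confirmation complies throughout.
- The injection risk is inferred: the sentence says study drug, which also covers oral lead-in and bridging tablets, to which the depot argument does not apply.
- Medical Monitor contact exists elsewhere, for choosing HAART (Section 1.3) and for interruptions in injections (Section 6.6.2).

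The defence fails on Section 1.3. That clause is conditional on withdrawal for virologic failure, is worded as a recommendation and refers to the Medical Monitor. But CVF makes withdrawal from treatment mandatory, and the clause ties HAART to confirmation, not to the resistance report. The Medical Monitor contacts concern choosing a new regimen or interrupting injections; none is required before giving the next injection under the permission. Section 6.6.2 does warn about interrupting ART, but starting HAART at confirmation leaves no gap.

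**Conclusion.** The point holds in limited form. Section 7.1.4.3 is internally inconsistent, and its permission conflicts with the HAART timing in Section 1.3. It sits poorly with Sections 2.3.1 and 7 without contradicting a stated day. The permission has an event-based end but no calendar limit, and it leaves room for a further LA injection.

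The expected size is small: about 0 to 1 of 135 participants, assuming the LATTE-2 Q4W snapshot rate is a fair guide. Harm further requires the investigator to use the discretion and an injection to fall due before the result. No primary endpoint is affected. It should still be corrected, because the consequence for the individual is irreversible and the delay does not alter the decision to stop.

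**What to change.** Replace the permission in Section 7.1.4.3, including its requirement to discontinue from the study once results arrive, with:

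> *No further CAB LA or RPV LA is given after the confirming HIV-1 RNA result; oral HAART, discussed with the Medical Monitor, starts as soon as failure is confirmed and is adjusted if needed when resistance results arrive. Participants who have received at least one dose of CAB LA or RPV LA are discontinued from study intervention and enter LTFU; participants who have received only oral study drug are discontinued and complete the Withdrawal visit.*

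The second sentence is needed because the present text discontinues the participant from the study, while the opening of the same section keeps injected participants in it. Sending everyone to LTFU would also be wrong, since Sections 1.3, 7.1 and 7.1.4.3 reserve it for those with at least one LA dose.

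The cost is wording in one section, with no new visit, test or data field. As a change to dosing rules it would go through a protocol amendment with IRB/IEC approval (Section 10.1.1), so it could be bundled with the next one.
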